3.1.3. Post-PMT Administration monitoring: Bedside for 60 Minutes

Subjects will be monitored at 30 and 60 minutes following completion of PMT administration. Subjects will be visually observed for signs of aspiration or other respiratory distress (PMT-002 and PMT-003), abdominal pain, vomiting, other signs of allergic reaction, and changes in vital signs (PMT-001, PMT-002, and PMT-003). Vital signs (temperature, heart rate, respiratory rate, blood pressure, and oxygen saturation) will be checked. The following vital sign changes will be recorded if observed, and will prompt notification of the primary clinical care team: (1) heart rate

increase or decrease by greater than or equal to 30 beats per minute; (2) respiratory rate increase or decrease by greater than or equal to 10 breaths per minute or if respiratory rate drops below 10 or increases above 25 (if respiratory rate not already outside these ranges); (3) temperature: increase or decrease by greater than or equal to 2 degrees Fahrenheit, or if temperature drops below 96°F or increases above 100.4°F (if temperature not already outside these ranges); (4) oxygen saturation decrease by greater than or equal to 5% (sustained for more than 20 seconds) or if oxygen saturation drops below 90% (on current amount of oxygen delivered, sustained for more than 20 seconds); (5) blood pressure decrease by more than 30 mmHg systolic or 15 mmHg diastolic, or if blood pressure drops below 90/60 (if blood pressure not already outside these ranges).

3.1.4. Post-PMT Administration Follow-Up

Following a subject's final PMT administration, subjects enter the follow up phase. During this phase, the following will occur: (1) if subjects are inpatient, daily maximum temperature, number of bowel movements, and any episodes of emesis will be recorded (based on electronic medical record) for 7 calendar days post-FMT; (2) in preparation for discharge from the hospital, subjects will record daily temperature, number of bowel movements, and any episodes of emesis for 7 days post last FMT (all subjects will be given a symptom diary card; a digital thermometer will also be provided); (3) subjects will be contacted by telephone or in- person for an interview focused on potential adverse events at 7 days (or next working day, not to exceed 10 days) after final FMT; (4) subjects will be contacted by telephone or in-person at 30 days (+/- 3 days) after final FMT for an interview focused on potential adverse events; (5) subjects will be contacted by telephone or in-person at 56 days (+/- 7 days) after final FMT for an interview focused on the primary outcome and adverse events; (6) subjects will be contacted by telephone or in-person at 90 days (+/- 7 days) after final FMT for an interview focused on potential adverse events; (7) subjects will be contacted by telephone or in-person at 180 days (+/- 7 days) after final FMT for an interview focused on potential adverse events.

Telephone versus in-person follow-up will be determined based on subject preference. (If subjects prefer to be seen in person, but have been discharged from the hospital, a clinic visit with a study team member will be arranged). Subjects enrolled as outpatients will have at least one in-person follow-up visit scheduled between 1- and 4-weeks post-FMT. All FMT recipients (or their surrogates) will be given contact information for the study coordinator. As detailed above, subjects will be followed for 180 days following last investigational product administration. All subjects will be also provided a study contact telephone number on a copy of the informed consent form, in case concerns for adverse event or other questions arise. Subjects will also be permitted to initiate electronic communication with the study team, although planned follow up visits will be conducted by telephone or in person. The study team may reach out to subjects electronically if difficulties arise in reaching the subject by telephone in order to schedule visits, but study-related questions will not be asked electronically. Subjects will be classified as lost to follow up if at least three attempts are made at contact without success; however, medical record review will still be used to obtain follow up information on these subjects. If a subject is eligible and enrolled a second (or greater) time, then their subsequent

follow up will be conducted according to the schedule set by their most recent enrollment, and any remaining follow ups from earlier enrollment(s) will not be performed.

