3.1.2. Study Intervention Phase

R-CDI trial interventions may be performed inpatient or outpatient at the listed study sites in [section 4.5](#). Once subjects are enrolled and informed consent is obtained, subjects will be assessed for their ability to tolerate oral capsules, gastric/duodenal/jejunal infusion, and enema (per active prescribed medication list and/or opinion of referring care provider); the subject's preference and the guidance of the referring care provider will determine if PMT-001, PMT-002, or PMT-003 will be used. Following this, stratified randomization to single- or double-dose strategy will be performed within route of delivery groups (i.e., within PMT-001, PMT-002, or PMT-003 groups). Administration of a single dose of the product will take place over 10 to 90 minutes (target 30 minutes). A second dose will be given between 4 and 24 hours after the first dose. The route of administration may be different for the second dose per subject's treating physician and subject preference. If a subject is unable to take at least 50% of a dose, they will be permitted to opt to receive a different route of administration for one dose within 24 hours. Any antibiotics previously prescribed for the treatment of CDI will be stopped 12-48 hours (target 24 hours) prior to the intervention.

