3.2.3.2. Post-PMT Administration Follow-Up

Safety endpoints assessed at the 7-day follow-up and all subsequent follow-ups will include fever, diarrhea, nausea, and vomiting. Safety endpoints assessed at the 30-day, 56-day, 90-day, and 180-day follow-ups will include evidence of new metabolic disease, including hyperglycemia, thyroid disease, weight gain or loss.

4. Study Population and Duration of Participation

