6.2.3. Post-Intervention 60 minutes

Subjects will be monitored for a period of 60 minutes following completion of each PMT administration. Subjects will be visually observed for signs of aspiration or other respiratory distress, abdominal pain, vomiting, other signs of allergic reaction, and changes in vital signs. Vital signs (temperature, heart rate, respiratory rate, blood pressure, and oxygen saturation) will be checked immediately post-administration and at 30 and 60 minutes following completion of PMT administration. The following vital sign changes will be recorded if observed, and will prompt notification of the primary clinical care team: (1) increase or decrease by greater than or equal to 30 beats per minute; (2) respiratory rate increase or decrease by greater than or equal to 10 breaths per minute or if respiratory rate drops below 10 or increases above 25 (if respiratory rate not already outside these ranges); (3) temperature: increase or decrease by greater than or equal to 2 degrees Fahrenheit, or if temperature drops below 96°F or increases above 100.4°F (if temperature not already outside these ranges); (4) oxygen saturation decrease by greater than or equal to 5% (sustained for more than 20 seconds) or if oxygen saturation drops below 90% (on current amount of oxygen delivered, sustained for more than 20 seconds); (5) blood pressure decrease by more than 30 mmHg systolic or 15 mmHg diastolic, or if blood pressure drops below 90/60 (if blood pressure not already outside these ranges).

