8.4.4. Safety Analysis

All subjects entered into the study and randomized will have detailed information collected on adverse events starting at enrollment and for the duration of follow-up, as described elsewhere. The primary safety endpoints of frequency of AEs, SAEs, and AESIs will be described.

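### The daily temperature, stool and emesis record is tied to the last dose, so the double-dose arm alone lacks it for the 4–24 h between doses, and solicited events there may be under-counted

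*Combined protocol and SAP*

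**What the plan says.** Section 3.1.4 opens the follow-up phase at the last dose: "Following a subject's final PMT administration, subjects enter the follow up phase". Within that phase the diary rule is that "subjects will record daily temperature, number of bowel movements, and any episodes of emesis for 7 days post last FMT". Section 6.3.1 repeats it, and section 7.6 also ties the diary to the last FMT. For inpatients the same three items "will be recorded (based on electronic medical record) for 7 calendar days post-FMT". That clause stands in the same phase but omits the word last.

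For the double-dose arm, section 3.1.2 says: "A second dose will be given between 4 and 24 hours after the first dose".

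Bedside observation applies to every dose. Section 6.2.3 says: "Subjects will be monitored for a period of 60 minutes following completion of each PMT administration". Vital signs "will be checked immediately post-administration and at 30 and 60 minutes following completion of PMT administration".

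Section 3.2.3 makes the frequency of solicited adverse events a primary safety endpoint, and section 3.2.3.2 names the symptoms: "Safety endpoints assessed at the 7-day follow-up and all subsequent follow-ups will include fever, diarrhea, nausea, and vomiting". Under section 8.4.4, all randomized subjects "will have detailed information collected on adverse events starting at enrollment and for the duration of follow-up". The same section plans only a description of the safety frequencies, with no test between arms.

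**The concern.** The trial compares one dose with two, and early reactions are part of what a reader will want to compare. Fever, loose stools and vomiting are what the daily record measures, and they feed a primary safety endpoint. Because the record is tied to the last dose, its start relative to first exposure depends on the arm. A single-dose subject's record follows the only dose. A double-dose subject's record follows the second dose and skips the interval after the first.

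At stake is whether the described frequencies of solicited events can be read side by side. If reactions after the first of two doses are picked up less reliably than reactions after a single dose, a true excess with double dosing would look smaller than it is. The primary efficacy endpoint, the sample size and the type I error are not involved.

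**Working it through.** The protocol states no figure for this point, so there is nothing to reproduce. The check is arithmetic on the observation windows, followed by an illustration under assumed risks.

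**Inputs**
- Interval between doses: 4 to 24 h (3.1.2).
- Bedside observation after each dose: 1 h (6.2.3).
- Duration of one administration: 10 to 90 min (3.1.2, 5.7).
- Diary: 7 days = 168 h after the last dose (3.1.4).
- Target enrollment 300 (4.5), randomized 1:1 (3.1.5): 300 / 2 = 150 per arm.

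**Time without the structured record, double-dose arm**
- Between doses: 4 to 24 h.
- After the bedside hour, interval counted from the end of dose 1: 4 − 1 = 3 h to 24 − 1 = 23 h.
- Interval counted from the start of dose 1: shortest 4 − 1.5 − 1 = 1.5 h; longest 24 − 10/60 − 1 ≈ 22.8 h.
- As a share of the time from first dose to diary end: 4 / (168 + 4) = 2.3% to 24 / (168 + 24) = 12.5%.

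Section 7.6 has temperature taken once a day, so the practical loss is about one daily entry at most. With a short interval, both doses may fall on one calendar day.

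**What covers those hours instead**
- Table 2 places an adverse event check at the intervention. It schedules symptom and vital-sign review at 30 and 60 minutes, and next at 7 days after the final intervention.
- Adverse events are collected from enrollment (8.4.4) and reported from consent (9.3).
- Questioning is non-directive (9.2).
- Each visit is meant to look back to the previous one (6.5), and the chart is reviewed at day 7 (7.1).

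**Direction, illustrated**

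The protocol gives no reaction risks, so those used here are assumptions. Let p1 and p2 be the risks after doses 1 and 2, taken as independent. Let c be the share of dose-1 reactions in the double-dose arm that channels other than the diary catch. Assume full capture of single-dose reactions and of dose-2 reactions.

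Recorded double-dose risk = 1 − (1 − p1·c)(1 − p2). True risk is the same expression with c = 1.

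With p1 = p2 = 10%, the single-dose risk is 10%, the true double-dose risk is 1 − 0.9 × 0.9 = 19%, and the true excess is 9 points:

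| c | Recorded double-dose risk | Recorded excess |
|---|---|---|
| 0 | 1 − 1 × 0.9 = 10% | 0 points |
| 0.5 | 1 − 0.95 × 0.9 = 14.5% | 4.5 points |
| 1 | 19% | 9 points |

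With p2 = 5%, the true double-dose risk is 1 − 0.9 × 0.95 = 14.5%. Recorded risk is 5% at c = 0 and 1 − 0.95 × 0.95 = 9.75% at c = 0.5, against 10% with a single dose.

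Taken alone, then, the gap leaves the excess intact or shrinks it. Double dose looks better than single dose only if the second dose is assumed to cause fewer reactions and capture is also low.

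**The case against.** A reader might infer that the hours after the first of two doses go unrecorded. The protocol does not support that. Those hours begin with a bedside period that includes three vital-sign checks. Adverse events are collected from enrollment, and the day-7 visit looks back with chart review. What is missing is the structured daily record, not all recording.

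A reader might also infer that the safety comparison favours double dose. That is not supported either. Double-dose subjects have a second bedside hour and a second in-person contact 4 to 24 h after the first dose, and section 9.2 has adverse events sought at each contact. Single-dose subjects have no scheduled contact at that point, so some ascertainment runs the other way. With equal per-dose risks, even zero capture outside the diary gives equal recorded risks, not an advantage for two doses. No between-arm safety test is planned.

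Three further points stand. The protocol does not give the hour at which the diary starts, so complete coverage of the single-dose arm's first day is not established. Hourly percentages of that day suit a once-daily record poorly. For inpatients the clause lacks the word last and the data come from the chart, so values from the hours after dose 1 may be retrievable.

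What the objection does not remove is the difference in the rule itself. Non-directive recall about a week later is weaker than a prospective daily record, and the stated anchor withholds that record between doses in one arm only.

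**Conclusion.** The point holds in a limited form. Tying the daily record to the last dose creates an arm-dependent gap in structured recording of 4 to 24 h, or about 3 to 23 h after the bedside hour when the interval runs from the end of dose 1. That is roughly one diary entry per affected subject. It may under-count solicited events after the first of two doses and shrink a true excess. How far depends on how much the other channels catch, and the net direction of ascertainment cannot be settled from the protocol.

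Up to about 150 subjects are affected. The number may be smaller because the start of the inpatient window is ambiguous. The consequence is confined to the descriptive safety analysis. The percentages in the illustration rest on assumed risks and show direction only. The change is worth making because it is cheap and removes a difference between arms that serves no purpose.

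**What to change.** In sections 3.1.4, 6.3.1 and 7.6, start both the subject diary and the inpatient chart abstraction on the day of the first PMT administration in both arms, and continue them to 7 days after the last dose. Use the same anchor wording for inpatients and outpatients, which also removes the ambiguity in the inpatient clause. In section 8.4.4, state that fever, emesis and stool frequency will be described by arm from the first dose to 7 days after the first dose, so that both arms are read on the same clock.

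A separate report for the 24 h after each dose is not proposed, because a once-daily diary cannot separate doses given 4 to 24 h apart.

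The cost is about one extra diary day in the double-dose arm and earlier hand-out of the diary and thermometer. No visits are added, and sample size, power and type I error do not change.

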3.1.5. Allocation to Interventional Group

Stratified randomization will be performed in a 1:1 fashion (one to single-dose and one to double-dose). The stratification will be by route of delivery, which will be decided on following enrollment but prior to randomization. The route of administration (i.e., PMT-001 versus PMT-002 versus PMT-003) will be determined by counsel from the subject's referring health care provider and the subject's own preference. The randomization strata will include: upper delivery (PMT-002 or PMT-003) or lower delivery (PMT-001). Stratified randomization by route will be performed in order to ensure balance in route of delivery between the two groups. The randomization schedule will be prepared using a random-size block strategy to ensure balance throughout the trial. Prior to enrollment of the first subject, a randomization table will be produced for each category using Stata statistical software and the "Ralloc" package. There is no randomization to a no-FMT control because FMT is already guideline-recommended for the treatment of R-CDI (McDonald 2018).

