2.3. Exploratory Objective

To characterize differences in efficacy of fecal microbiota transplantation for R-CDI based on (1) route of administration, (2) unique bacterial community features of the administered PMT dose, and (3) features of host immune response to CDI.

3. Investigational Plan

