8.3. Sample Size and Power Determination

The primary analysis will be stratified based on the most recent positive CDI test (NAAT versus EIA) prior to enrollment. Given the anticipated enrollment of 300 subjects (150 per intervention group), a conservative estimate that 10% of subjects will be lost to follow-up (i.e., minimum subject number 90% of total), and the expectation that the ratio of EIA-positive/NAAT-positive subjects will be 1:2, the expected sample size will be 90 for EIA and 180 for NAAT ($150*0.9=135$ per arm, with a 45:90 ratio for EIA/NAAT). The low-dose cure rate is anticipated to be about 50% in the NAAT group and 70% in the EIA group. Based on these assumptions, the detectable difference between the cure rates for the low and high dose groups for 80% power and varying type I error rates, based on a Chi-square test (two-sided), are provided below.

Stratified Population	Number of subjects (subjects per arm)	Type 1 Error	Power	Detectable difference in proportions compared to 50%
EIA	90 (45)	0.05	0.8	0.7725
EIA	90 (45)	0.1	0.8	0.7458
EIA	90 (45)	0.2	0.8	0.7133
NAAT	180 (90)	0.05	0.8	0.7003
NAAT	180 (90)	0.1	0.8	0.6793
NAAT	180 (90)	0.2	0.8	0.6543

For phase II studies it is typical to accept a type 1 error of greater than 0.05 (Schoenfeld 1980; Khan 2012). For this phase II study, we will accept a difference between intervention groups that meets a type I error threshold of 0.2. Therefore, we will have 80% power to detect a difference of 0.2133 (50% to 71.33%) in the EIA group, and a difference of 15.43% (50% to 65.43%) in the NAAT group. The power calculations were performed using PASS 16 (Power Analysis and Sample Size Software (2018). NCSS, LLC. Kaysville, Utah, USA, ncss.com/software/pass/).

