8.4.2. Efficacy Analysis

An intention to treat analysis will be performed for the primary outcome of clinical resolution of diarrhea without recurrence in subjects with R-CDI at 8 weeks following FMT. A logistic regression model will be used to compare the two study groups (single-dose versus double-dose) to detect superiority of a dose. A p-value (one-sided) of <0.2 will be considered significant. As above, the primary analysis will be stratified based on the most recent positive CDI test (NAAT versus EIA) prior to enrollment. Per protocol analysis will also be performed, based on received (rather than randomized) treatment.

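### The primary logistic model in 8.4.2 leaves out route stratum, the only randomization factor (3.1.5); the test stays valid and the power at stake is small

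*Combined protocol and SAP*

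**What the plan says.** Section 3.1.5 stratifies randomization by route and by nothing else. It gives the reason: "Stratified randomization by route will be performed in order to ensure balance in route of delivery between the two groups". It lists two strata: "The randomization strata will include: upper delivery (PMT-002 or PMT-003) or lower delivery (PMT-001". Route is a baseline variable, "which will be decided on following enrollment but prior to randomization".

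Section 8.4.2 specifies the primary comparison: "A logistic regression model will be used to compare the two study groups (single-dose versus double-dose) to detect superiority of a dose". The threshold is "A p-value (one-sided) of <0.2 will be considered significant". On strata, it says "the primary analysis will be stratified based on the most recent positive CDI test (NAAT versus EIA) prior to enrollment". Test type is not a randomization factor, and no section puts route in this model.

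Elsewhere, route is an exploratory question in 2.3: "To characterize differences in efficacy of fecal microbiota transplantation for R-CDI based on (1) route of administration". Section 8.4.5, on exploratory analyses, gives no method for it. Section 3.1.2 allows the second dose to go by a different route. Its parenthesis describes randomization within three product groups, where 3.1.5, to which 6.1.5 defers, has two strata.

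**The concern.** The plan forces balance on route and asks whether efficacy differs by route, yet compares the arms as if route were not there. When a balanced factor predicts the outcome, a test that ignores it uses a variance that is too large for the design: it rejects less often than its nominal level under the null and loses some power. What is at stake is therefore efficiency, and whether the adjustment is fixed before the data are seen. The second matters because the trial is open label and because received route can differ from the stratum after randomization.

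**Working it through.** **Inputs from the documents.** From 8.3: "the expected sample size will be 90 for EIA and 180 for NAAT", that is 45 and 90 per arm, or 135 per arm in all; anticipated single-dose cure 50% (NAAT) and 70% (EIA); detectable rates 71.33% (EIA) and 65.43% (NAAT), each against 50%. From 8.4.2: one-sided 0.20.

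**Assumed, because the documents are silent.** Share of subjects in the lower stratum 50%, 25% or 10%; gap in cure between routes 0 to 30 points.

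**1. The plan's own figure.** With SE = √{[p₁(1−p₁) + p₂(1−p₂)]/n}:
- EIA: SE = √[(0.25 + 0.7133×0.2867)/45] = 0.1005; 0.2133/0.1005 = 2.12; 2.12 − 1.28 = 0.84, so power is 0.80.
- NAAT: SE = √[(0.25 + 0.6543×0.3457)/90] = 0.0727; 0.1543/0.0727 = 2.12, so power is again 0.80.

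Both match 8.3 at two-sided 0.2. Route plays no part. The implied odds ratios against 50% are 0.6543/0.3457 = 1.89 (NAAT) and 0.7133/0.2867 = 2.49 (EIA).

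**2. Size, by hand.** With lower share w, overall cure p and gap g, balance on route removes w(1−w)g² from the outcome variance p(1−p), but the unadjusted test does not know this. Its actual one-sided size is 1 − Φ(0.8416/√k), where k = 1 − w(1−w)g²/[p(1−p)]. At p = w = 0.5, k = 1 − g²:
- g = 0.10: k = 0.99, size 0.199
- g = 0.20: k = 0.96, size 0.195
- g = 0.30: k = 0.91, size 0.189

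**3. Model with both test types, by simulation.** 135 per arm, arms balanced within route, test type random at 1:2 EIA:NAAT, single-dose cure 50% and 70%. Wald test of dose, adjusted for NAAT/EIA, without and with route; 40,000 trials per scenario; equal routes. The Monte Carlo SE of size is 0.002. Gains were taken before rounding.

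| Route gap (points) | Size without / with | Power at OR 1.5, without / with (%) | Gain (points) | Gain at OR 1.89 and 2.49 (points) | SE of log OR at OR 1.5, with route |
|---|---|---|---|---|---|
| 0 | 0.199 / 0.199 | 77.6 / 77.7 | 0.1 | 0.0 | 0.258 |
| 10 | 0.204 / 0.205 | 76.9 / 77.2 | 0.2 | 0.0 | 0.259 |
| 20 | 0.197 / 0.202 | 76.1 / 76.7 | 0.6 | 0.2 | 0.263 |
| 30 | 0.192 / 0.202 | 74.1 / 75.4 | 1.3 | 0.3 | 0.269 |

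Repeat runs agree: the gain at OR 1.5 is about 0.5 at a 20-point gap and 1.3 at 30, and the gain at the 8.3 odds ratios never exceeds 0.4, on power of 96-97%. The SE without route is 0.257. It rises when route is added, because the conditional odds ratio lies further from 1. The benefit is in power and in recovering nominal size, not in a smaller SE.

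**4. Sensitivity at OR 1.5, gaps 0/10/20/30.**
- Routes 25:75: gain 0.1/0.2/0.5/1.2
- Routes 10:90: gain 0.0/0.1/0.3/0.5
- All 300 randomized subjects, equal routes: gain 0.1/0.1/0.5/1.2

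If the lower route is the better one, gains are similar or smaller.

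**5. Separate tests, one-sided 0.20, equal routes.**
- NAAT (90 per arm, 50% to 65.43%): change in power −0.2/−0.1/+0.4/+1.4.
- EIA (45 per arm, 50% to 71.33%): about −1.3 at gaps of 0 and 10, −0.7 at 20, and around zero at 30.
- EIA from the anticipated 70%, with an assumed 87% on two doses: from about −0.1 with no gap to between +1.2 and +1.7 at 30.

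Part of the EIA loss at 50% is discreteness: the unadjusted Wald test there has size about 0.23, against 0.20 to 0.21 with route.

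**The case against.** Section 8.4.2 lists no covariates at all, so the omission is read from silence. The stated purpose of stratifying is balance, and the design delivers balance whether or not route is modelled. No figure in the documents says that route affects cure. OR 1.5 is not in the plan; at the plan's own detectable effects the gain is close to nil. Section 8.3 powers EIA and NAAT separately, and if they are tested separately, adding route can cost power in EIA. All of this stands. It makes the point a refinement, not an error.

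Three limits on the figures also stand. The EIA odds ratio of 2.49 comes from a 50% base but is applied to 70% in the model with both test types. The EIA loss of 1.3 points belongs to the 50% base and nearly vanishes at 70%. And the unadjusted EIA-only test exceeds 0.20 at a 50% cure rate, but from small numbers, not from leaving out route.

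What the objection does not remove is that the stratum is known before randomization, costs nothing to include, and is better fixed now than chosen later.

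A reader might infer that ignoring a randomization factor makes the primary test biased or invalid, or seriously underpowered. The documents do not support that: with route balanced by design, the error is on the conservative side, and the loss is at most a point or so unless route gaps are very large. Nor do the two descriptions in 3.1.2 and 3.1.5 show that randomization is undefined. Section 6.1.5 defers to 3.1.5, which states the two strata, so this is a wording point.

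**Conclusion.** The point holds as a minor one about efficiency and prespecification. Nothing is lost if route does not predict cure. If it does, the NAAT/EIA-adjusted test without route runs at about 0.19 instead of 0.20 at a 30-point gap. The power forgone is negligible at the effects implied by 8.3 and only about a point at OR 1.5 with a gap that large. For EIA alone the change can go either way. These sizes rest on assumed route shares, route gaps and, away from 8.3, assumed treatment effects; none of these can be checked in the documents.

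**What to change.** In 8.4.2, add the pre-randomization route stratum, coded upper/lower as in the randomization table, as a prespecified covariate in the primary logistic model alongside NAAT/EIA. State that received or second-dose route is not used.

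If EIA and NAAT are tested separately, state in advance whether route enters each model, and do not let the data decide. One option is to include it in the model containing both test types and leave it out of the EIA-only model. The reason is estimability: with 90 EIA subjects, 70% cure and an assumed 10:90 route split, all or none of the lower-route subjects would be cured in 6.5% of trials with no gap, and in 34% if the lower route were 20 points better.

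This change does not settle whether the primary test is pooled or separate by test type; 8.4.2 has to say that in its own right. Show cure proportions by arm beside the odds ratio, which becomes conditional on route as well as test type. As a wording correction, reconcile the three product groups in 3.1.2 with the two strata in 3.1.5.

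The cost is one covariate, a few sentences in 8.4.2 and one edit in 3.1.2. No new data or subjects are needed.
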